
General Considerations	
Dose Modifications	Toxicity Management

IP Note: IP/study regimen should be permanently discontinued in Grade 3 events with high likelihood for morbidity and/or mortality – e.g., myocarditis, or other similar events even if they are not currently noted in the guidelines. Similarly, consider whether IP/study regimen should be permanently discontinued in Grade 2 events with high likelihood for morbidity and/or mortality – e.g., myocarditis, or other similar events even if they are not currently noted in the guidelines – when they do not rapidly improve to Grade <1 upon treatment with systemic steroids and following full taper
 
Note: There are some exceptions to permanent discontinuation of IP for Grade 4 events (i.e., hyperthyroidism, hypothyroidism, Type 1 diabetes mellitus).
	
for specific type of immunosuppressive) should be considered for events not responding to systemic steroids. Progression to use of more potent immunosuppressives should proceed more rapidly in events with high likelihood for morbidity and/or mortality – e.g., myocarditis, or other similar events even if they are not currently noted in the guidelines – when these events are not responding to systemic steroids.
 
 
– With long-term steroid and other immunosuppressive use, consider need for Pneumocystis jirovecii pneumonia (PJP, formerly known as Pneumocystis carinii pneumonia) prophylaxis, gastrointestinal protection, and glucose monitoring.
 
 
Discontinuation of IP/study regimen is not mandated for Grade 3/Grade 4 inflammatory reactions attributed to local tumor response (e.g., inflammatory reaction at sites of metastatic disease and lymph nodes). Continuation of IP/study regimen in this situation should be based upon a benefit-risk analysis for that subject.

AE Adverse event; CTC Common Toxicity Criteria; CTCAE Common Terminology Criteria for Adverse Events; imAE immune-mediated adverse event; IV intravenous; NCI National Cancer Institute; PO By mouth.

Specific Immune-Mediated Reactions			
Adverse Events	Severity Grade of the Event (NCI CTCAE version 4.03)	Dose Modifications	Toxicity Management

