Hepatitis (elevated LFTs) Infliximab should not be used for management of immune-mediated hepatitis.	Any Grade	General Guidance	For Any Grade: 
 
Monitor and evaluate liver function test: AST, ALT, ALP, and TB.
 
Evaluate for alternative etiologies (e.g., viral hepatitis, disease progression, concomitant medications).
 

	Grade 1 (AST or ALT >ULN and ≤3.0×ULN and/or TB > ULN and ≤1.5×ULN)	
 
No dose modifications.
 
If it worsens, then treat as Grade 2 event.
 
	For Grade 1: 
 
Continue LFT monitoring per protocol.
 

	Grade 2 (AST or ALT >3.0×ULN and ≤5.0×ULN and/or TB >1.5×ULN and ≤3.0×ULN)	
 
Hold IP/study regimen dose until Grade 2 resolution to Grade ≤1.
 
If toxicity worsens, then treat as Grade 3 or Grade 4.
 
If toxicity improves to Grade ≤1 or baseline, resume IP/study regimen after completion of steroid taper.
 
	For Grade 2: 
 
Regular and frequent checking of LFTs (e.g., every 1 to 2 days) until elevations of these are improving or resolved.
 
If no resolution to Grade ≤1 in 1 to 2 days, consider, as necessary, discussing with study physician.
 
If event is persistent (>3 to 5 days) or worsens, promptly start prednisone 1 to 2 mg/kg/day PO or IV equivalent.
 
If still no improvement within 3 to 5 days despite 1 to 2 mg/kg/day of prednisone PO or IV equivalent, consider additional work up and start prompt treatment with IV methylprednisolone 2 to 4 mg/kg/day.
 
If still no improvement within 3 to 5 days despite 2 to 4 mg/kg/day of IV methylprednisolone, promptly start immunosuppressives (i.e., mycophenolate mofetil).a Discuss with study physician if mycophenolate mofetil is not available. Infliximab should NOT be used.
 
Once the subject is improving, gradually taper steroids over ≥28 days and consider prophylactic antibiotics, antifungals, and anti-PJP treatment (refer to current NCCN guidelines for treatment of cancer-related infections [Category 2B recommendation]).a
 

**PLEASE SEE shaded area immediately below this section to find guidance for management of “Hepatitis (elevated LFTS)” in HCC patients**

Specific Immune-Mediated Reactions			

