Adverse Events	Severity Grade of the Event (NCI CTCAE version 4.03)	Dose Modifications	Toxicity Management
	
Grade 3 or 4                      (Grade 3: AST or ALT >5.0×ULN and ≤20.0×ULN and/or TB >3.0×ULN and ≤10.0×ULN)
 
(Grade 4: AST or ALT >20×ULN and/or TB >10×ULN)
	
For Grade 3:                      For elevations in transaminases ≤8 × ULN, or elevations in bilirubin ≤5 × ULN:
 
 
• Hold IP/study regimen dose until resolution to Grade ≤1 or baseline
 
• Resume IP/study regimen if elevations downgrade to Grade ≤1 or baseline within 14 days and after completion of steroid taper.
 
• Permanently discontinue IP/study regimen if the elevations do not downgrade to Grade ≤1 or baseline within 14 days
 
 
For elevations in transaminases >8 × ULN or elevations in bilirubin >5 × ULN, discontinue IP/study regimen.
 
Permanently discontinue IP/study regimen for any case meeting Hy’s law criteria (AST and/or ALT >3 × ULN + bilirubin >2 × ULN without initial findings of cholestasis (i.e., elevated alkaline P04) and in the absence of any alternative cause.b
 
For Grade 4:                      Permanently discontinue IP/study regimen.
	
For Grade 3 or 4:
 
 
– Promptly initiate empiric IV methylprednisolone at 1 to 4 mg/kg/day or equivalent.
 
– If still no improvement within 3 to 5 days despite 1 to 4 mg/kg/day methylprednisolone IV or equivalent, promptly start treatment with immunosuppressive therapy (i.e., mycophenolate mofetil). Discuss with study physician if mycophenolate is not available.
 
 
Infliximab should NOT be used.
 
 
– Perform hepatology consult, abdominal workup, and imaging as appropriate.
 
– Once the subject is improving, gradually taper steroids over ≥28 days and consider prophylactic antibiotics, antifungals, and anti-PJP treatment (refer to current NCCN guidelines for treatment of cancer-related infections [Category 2B recommendation]).a
 

Specific Immune-Mediated Reactions			
Adverse Events	Severity Grade of the Event (NCI CTCAE version 4.03)	Dose Modifications	Toxicity Management

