
Hepatitis (elevated LFTs)                      Infiximab should not be used for management of immune-mediated hepatitis.
 
 
THIS shaded area is guidance only for management of “Hepatitis (elevated LFTs)” in HCC patients
 
 
See instructions at bottom of shaded area if transaminase rise is not isolated but (at any time) occurs in setting of either increasing bilirubin or signs of DILI/liver decompensation
	Any Grade	
General Guidance
	
For Any Grade:
 
 
- Monitor and evaluate liver function test: AST, ALT, ALP, and TB.
 
- Evaluate for alternative etiologies (e.g., viral hepatitis, disease progression, concomitant medications, worsening of liver cirrhosis [e.g., portal vein thrombosis]).
 
- For HBV+ subjects: evaluate quantitative HBV viral load, quantitative HBsAg, or HBeAg
 
- For HCV+ subjects: evaluate quantitative HCV viral load
 
- Consider consulting hepatologist/Infectious disease specialist regarding change/implementation in/of antiviral medications for any subject with an elevated HBV viral load >2000 IU/ml
 
- Consider consulting hepatologist/Infectious disease specialist regarding change/implementation in/of antiviral HCV medications if HCV viral load increased by ≥2-fold
 
- For HCV+ with HBcAB+: Evaluate for both HBV and HCV as above
 

	
Grade 1                      (Isolated AST or ALT >ULN and ≤5.0×ULN, whether normal or elevated at baseline)
	
 
• No dose modifications.
 
• If ALT/AST elevations represents significant worsening based on investigator assessment, then treat as Grade 2 event.
 
 
For all grades, see instructions at bottom of shaded area if transaminase rise is not isolated but (at any time) occurs in setting of either increasing bilirubin or signs of DILI/liver decompensation
	

Specific Immune-Mediated Reactions			
Adverse Events	Severity Grade of the Event (NCI CTCAE version 4.03)	Dose Modifications	Toxicity Management

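### Appendix M prints the Hy's law permanent stop only under Grade 3, but its limits are already met within Grade 2, where the instruction is to hold and then resume

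*Protocol*

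**What the plan says.** Protocol Section 7.2.2.2 sends durvalumab dose modification to Appendix M. In the non-HCC hepatitis table there, Grade 2 is AST or ALT above 3 and up to 5 × ULN and/or total bilirubin above 1.5 and up to 3 × ULN. The Grade 2 dose-modification cell gives three instructions: hold until the event returns to Grade 1 or lower; "If toxicity worsens, then treat as Grade 3 or Grade 4"; and "If toxicity improves to Grade ≤1 or baseline, resume IP/study regimen after completion of steroid taper". It does not mention Hy's law.

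The Hy's law rule is printed once in this table, in the combined Grade 3 or 4 row, after the Grade 3 sub-heading and before the Grade 4 one: "Permanently discontinue IP/study regimen for any case meeting Hy’s law criteria". The limits given with it are AST and/or ALT above 3 × ULN plus bilirubin above 2 × ULN, "without initial findings of cholestasis (i.e., elevated alkaline P04) and in the absence of any alternative cause".

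The Any Grade row of the same table asks sites to monitor AST, ALT, ALP and bilirubin, and to "Evaluate for alternative etiologies (e.g., viral hepatitis, disease progression, concomitant medications"). It contains no stopping instruction.

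**The concern.** The rule's AST/ALT limit is exactly the value at which Grade 2 starts, and its bilirubin limit lies inside the Grade 2 bilirubin band. Some subjects therefore meet the rule while still Grade 2 on both tests. For them the appendix gives two opposite instructions: resume after recovery (Grade 2 cell), or never resume (Grade 3 cell). A site that grades the event first and then reads its row is directed to the Grade 3 text only on worsening, so it need never see the stop.

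What is at stake is patient safety in the combination arm, namely rechallenge with durvalumab after a possible Hy's law case. The same text governs the optional extension: Appendix O sends dose management to Section 7.2.2, and so to Appendix M. There, monitoring is by site standard of care and only serious adverse events and pregnancies are reported to the sponsor, so the printed rule carries more weight.

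**Working it through.** The plan states no figure on this point, so the check compares limits.

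**Inputs** (Appendix M, non-HCC hepatitis table, in multiples of ULN):

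| Test | Grade 1 | Grade 2 | Grade 3 | Grade 4 |
|---|---|---|---|---|
| AST or ALT | >1 to 3 | >3 to 5 | >5 to 20 | >20 |
| Total bilirubin | >1 to 1.5 | >1.5 to 3 | >3 to 10 | >10 |

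Hy's law limits: AST/ALT >3 and bilirubin >2. Section 7.2.3 limits for starting the next cycle: AST/ALT ≤2.5 and bilirubin ≤1.5. Overall grade is taken as the worse of the two tests.

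**Where the limits fall**

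- Grade 0 or 1: AST/ALT is at most 3, so the limits cannot be met.
- Grade 2: they are met when AST/ALT is >3 to 5 and bilirubin is >2 to 3.
- Grade 3: the Hy's law sentence is in the cell that the site is reading.
- Grade 4: permanent discontinuation is already ordered.

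The gap is therefore confined to Grade 2.

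**Size of the overlap**

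On a 0.1 × ULN grid, both tests are Grade 2 at 20 AST/ALT values (3.1 to 5.0) by 15 bilirubin values (1.6 to 3.0): 20 × 15 = 300 cells. The Hy's law limits are exceeded at 20 × 10 = 200 of these (bilirubin 2.1 to 3.0), and 200/300 = 66.7%. This is the same as (3 − 2)/(3 − 1.5) = 1.0/1.5 of the bilirubin band.

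**Worked case**

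Onset: AST 4 and bilirubin 2.5 × ULN, normal alkaline phosphatase, no other cause found. This is Grade 2 on both tests, and 4 > 3 and 2.5 > 2, so the Hy's law limits are exceeded.

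- Rapid recovery to AST 0.9 and bilirubin 0.8: both normal. The Grade 2 resume line is met, and so is Section 7.2.3 (0.9 ≤ 2.5; 0.8 ≤ 1.5).
- Recovery to AST 2.0 and bilirubin 1.2: Grade 1 on both. The resume line and Section 7.2.3 (2.0 ≤ 2.5; 1.2 ≤ 1.5) are again met.

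**Whether other text closes the gap**

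- General Considerations in Appendix M: "Similarly, consider whether IP/study regimen should be permanently discontinued in Grade 2 events with high likelihood for morbidity and/or mortality", but only "when they do not rapidly improve to Grade" below 1. This is discretionary. It does not reach the first recovery above, and in the second it asks at most for consideration.
- Section 7.2.3 only delays the next cycle while tests remain raised. Its discontinuation provision concerns delays of more than 56 days.
- Discussion with the study physician in the Grade 2 row is left to the site's judgement.
- The HCC-only table does handle combined rises: "For all grades, see instructions at bottom of shaded area if transaminase rise is not isolated". The instructions it points to move a Grade 2 rise with rising bilirubin up to Grade 3 dosing. They do not apply to other subjects, and Section 4.2.2 excludes advanced malignant hepatic tumors.

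**The case against.** The best counter-argument is that the text already decides the case. The Hy's law sentence is worded to cover every case and prints its own numerical limits, so it is more specific than the general Grade 2 resume line and should prevail. It also overrides the resume line in the Grade 3 cell without saying so, and the same reading could be applied to Grade 2. In practice the drug is held at once, liver tests are repeated about every one to two days, and an investigator who has found raised transaminases and bilirubin and excluded cholestasis and other causes may well stop treatment anyway.

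The universal wording does suggest that an all-grade stop was intended, and the practical safeguards reduce the risk. But intent does not remove an unqualified, opposite instruction from the row that the site is told to follow. The Grade 3 comparison fails because there the stop and the resume line share a cell, so a reader sees both. The appendix elsewhere places such stops where they will be read: biopsy-proven myocarditis in the Any Grade row, and the Grade 2 stops for peripheral neuromotor syndromes and myositis in their own Grade 2 rows.

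It also stands that the two-thirds figure says nothing about how many patients are affected.

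**Conclusion.** The concern holds. For AST/ALT above 3 and up to 5 × ULN with bilirubin above 2 and up to 3 × ULN, the Grade 2 row read as written permits a restart of durvalumab that the same appendix forbids. The text should be corrected.

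The affected region is narrow. It requires no initial cholestasis and no alternative cause, and Section 4.2.2 recognises that ineffective erythropoiesis can raise bilirubin in these diseases, which could be such a cause. The documents give no frequency, so the number of subjects cannot be estimated. The conclusion rests on the printed grade bands and on a site applying the row for the grade it has assigned. No efficacy analysis, sample size or error rate changes.

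**What to change.** Put the stop in the Any Grade dose-modification cell of the non-HCC hepatitis table, the position already used for myocarditis. It should say that at every grade, AST and/or ALT above 3 × ULN with bilirubin above 2 × ULN, without initial cholestasis and with no other cause, means permanent discontinuation, and that this takes precedence over hold and resume in the grade rows. Alternatively, add the same rule as an explicit exception in the Grade 2 cell.

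The cost is a wording change in one row plus notification of sites. Written IRB/EC approval is needed before use if the change is treated as non-administrative (Section 13.5). Appendix M is a versioned durvalumab guideline (01 Nov 2017), so the sponsor should align the change with that source to avoid a local divergence. No procedures, visits or patients are added.

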For toxicity that is thought to be related to treatment with durvalumab, including immune-mediated adverse events (imAEs) or infusion-type reactions, as well as for nonimmune mediated reactions, the infusion of durvalumab may be slowed or interrupted, or a dose may be withheld, as described in Section 7.2.2.2. Dose reduction of durvalumab is not permitted.

In the event that a subject assigned to the combination treatment arm discontinues treatment with durvalumab or subcutaneous azacitidine because of drug-related toxicity, treatment with subcutaneous azacitidine or durvalumab monotherapy may continue until a discontinuation criterion is met (see Section 11.1). These subjects will be included in the ITT, safety and EE populations if they meet the respective criteria.

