### 7.2.1.2. Durvalumab Dispensation and Administration

Total in-use storage time from needle puncture of durvalumab vial to start of administration should not exceed 4 hours at room temperature or 24 hours at 2°C to 8°C (36°F to 46°F). If in-use storage time exceeds these limits, a new dose must be prepared from new vials. Durvalumab does not contain preservatives and any unused portion must be discarded.

Sites should follow standard and local aseptic procedures and instructions from the pharmacy manual for all activities. All dispensing activities should be documented according to local procedures. The shelf lives stated above are based on chemical and physical stability; assignment of microbial shelf life is the responsibility of the clinical center and should be aligned with local procedure for managing microbial risk as long as the times specified in this section are not exceeded. Vials should be used for the specific subjects to whom they are assigned, and must not be shared between subjects.

The preparation of infusion bags should be done under aseptic conditions by trained personnel; they should not be prepared on the ward.

Vials containing durvalumab may be gently inverted for mixing, but should not be shaken. All durvalumab vials should be equilibrated to room temperature for 30 minutes prior to dose preparation.

Subjects will receive durvalumab, 1500 mg intravenously on Day 1 of each 28-day treatment cycle by IV infusion over approximately 1 hour (± 5 minutes). Infusions of durvalumab may be interrupted, slowed, or discontinued in order to address toxicity, but dose reduction of durvalumab is not permitted (see Section 7.2.2.2).

Refer to the current durvalumab IB for detailed information about the physical properties of durvalumab and to the pharmacy manual for additional preparation, administration, or storage information.

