#### **Dose Modifications due to Nonhematological Toxicity**

Following receipt of any dose of subcutaneous azacitidine, subsequent cycles may be delayed if a certain level of toxicity occurs after the previous dose. Any subject who experiences a nonhematological AE with Common Terminology Criteria for Adverse Events (CTCAE Version 4.03) toxicity Grade 3 or 4 that is an escalation from his or her status at baseline (prior to the first dose) should have subcutaneous azacitidine temporarily discontinued until the toxicity grade returns to less than Grade 3. Subcutaneous azacitidine should be permanently discontinued if nonhematological toxicity persists at Grade 3 or 4 for more than 21 days, despite the temporary interruption of subcutaneous azacitidine.

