#### 7.2.2.2. Durvalumab

Please refer to [Appendix M](#) for detailed instructions for dose modifications and toxicity management.

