Grade 1 or 2	For Grade 1: The infusion rate of IP/study regimen may be decreased by 50% or temporarily interrupted until resolution of the event.  For Grade 2: The infusion rate of IP/study regimen may be decreased 50% or temporarily interrupted until resolution of the event. Subsequent infusions may be given at 50% of the initial infusion rate.	For Grade 1 or 2: 
 
– Acetaminophen and/or antihistamines may be administered per institutional standard at the discretion of the investigator.
 
– Consider premedication per institutional standard prior to subsequent doses.
 
– Steroids should not be used for routine premedication of Grade <math>\leq 2</math> infusion reactions.
 

Grade 3 or 4	For Grade 3 or 4: Permanently discontinue IP/study regimen.	For Grade 3 or 4: 
 
– Manage severe infusion-related reactions per institutional standards (e.g., IM epinephrine, followed by IV diphenhydramine and ranitidine, and IV glucocorticoid).
 

[figure not shown]
CTCAE Common Terminology Criteria for Adverse Events; IM intramuscular; IV intravenous; NCI National Cancer Institute.

Non-Immune-Mediated Reactions		
Severity Grade of the Event (NCI CTCAE version 4.03)	Dose Modifications	Toxicity Management
Any Grade	Note: Dose modifications are not required for AEs not deemed to be related to study treatment (i.e., events due to underlying disease) or for laboratory abnormalities not deemed to be clinically significant.	Treat accordingly, as per institutional standard.
Grade 1	No dose modifications.	Treat accordingly, as per institutional standard.
Grade 2	Hold IP/study regimen until resolution to ≤Grade 1 or baseline.	Treat accordingly, as per institutional standard.
Grade 3	Hold IP/study regimen until resolution to ≤Grade 1 or baseline. For AEs that downgrade to ≤Grade 2 within 7 days or resolve to ≤Grade 1 or baseline within 14 days, resume IP/study regimen administration. Otherwise, discontinue IP/study regimen.	Treat accordingly, as per institutional standard.
Grade 4	Discontinue IP/study regimen (Note: For Grade 4 labs, decision to discontinue should be based on accompanying clinical signs/symptoms, the Investigator’s clinical judgment, and consultation with the Sponsor.).	Treat accordingly, as per institutional standard.

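### Appendix M's Grade 3 row for non-immune reactions tells sites both to hold and to resume treatment when a related event has fallen only to Grade 2 within 7 days

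*Protocol*

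**What the plan says.** Protocol Section 7.2.2.2 contains no durvalumab rule of its own. It refers the reader to Appendix M "for detailed instructions for dose modifications and toxicity management". Section 3.2.2 confirms that events without an immune mechanism are covered: "as well as for nonimmune mediated reactions, the infusion of durvalumab may be slowed or interrupted, or a dose may be withheld".

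The Grade 3 row of the Non-Immune-Mediated Reactions table in Appendix M has three sentences:

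1. "Hold IP/study regimen until resolution to ≤Grade 1 or baseline"
2. "For AEs that downgrade to ≤Grade 2 within 7 days or resolve to ≤Grade 1 or baseline within 14 days, resume IP/study regimen administration"
3. "Otherwise, discontinue IP/study regimen"

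The Grade 2 row directly above carries the same hold instruction as sentence 1 and sets no time limit. A note at the top of the table exempts events judged unrelated to study treatment and laboratory abnormalities judged not clinically significant.

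Durvalumab dosing is monthly: "Subjects will receive durvalumab, 1500 mg intravenously on Day 1 of each 28-day treatment cycle".

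**The concern.** Sentence 1 ends the hold at Grade 1 or baseline. Sentence 2 tells the site to resume once the event is at Grade 2, provided that happens within 7 days. A subject can satisfy the second condition without satisfying the first, and the row does not say that sentence 2 is an exception to sentence 1.

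At stake is whether an Arm A subject whose related toxicity is still at Grade 2 receives the next durvalumab infusion. Two sites following the same page could act differently on the same event. The row also remains in force after the main study: Appendix O sends extension-phase dose modification back to Section 7.2.2, and so to Appendix M. In the extension, eCRF collection stops and only SAEs and pregnancies are reported to the sponsor, so inconsistent use of the row would be hard to detect.

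**Working it through.** The plan gives no figure to reproduce, so the check is a reading of the row against each course that an event can take.

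**Inputs.** The three sentences and the Grade 2 row come from Appendix M; the 28-day interval comes from Section 7.2.1.2. Days are counted from when the event reached Grade 3. That is an assumption, because the row does not name its starting point. The event is taken to be treatment-related, non-immune and not exempted by the table's note.

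| Course of the Grade 3 event | Sentence 1 | Sentences 2 and 3 | Result |
|---|---|---|---|
| (a) Grade 1 or baseline by day 7 | hold ends | resume | agree |
| (b) Grade 2 by day 7 and still Grade 2; baseline below Grade 2 | hold | resume | **conflict** |
| (c) Grade 3 at day 7; Grade 1 or baseline by day 14 | hold ends | resume | agree |
| (d) Grade 3 at day 7; Grade 2 at day 14; baseline below Grade 2 | hold target not reached | discontinue | no hold-versus-resume conflict |
| (e) Baseline Grade 2; back to Grade 2 within 14 days | baseline met, hold ends | resume | agree |

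Only course (b) is contradictory. The baseline condition matters: a subject who entered with the same finding at Grade 2 falls under (e), where the sentences agree.

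**When (b) changes a dose.** The next infusion falls on Day 28 + 1 = Day 29 of the current cycle. Two illustrative onset days show the effect of timing:

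- Onset on Day 24, at Grade 2 on Day 28 (4 days later, inside the 7-day window) and still Grade 2 on Day 29: the infusion is due while the sentences disagree.
- Onset on Day 5, at Grade 2 by Day 12 (5 + 7): the sentences disagree from then on, but an infusion is affected only if the event is still Grade 2 on Day 29, which is 29 − 5 = 24 days after onset.

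**Whether another provision settles it.**

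- Section 7.2.2.2 only points to Appendix M.
- Section 7.2.3 sets renal and hepatic limits for starting the next cycle and is silent on other toxicities.
- Section 7.2.2.1 concerns azacitidine. After a Grade 3 or 4 nonhematological event the subject "should have subcutaneous azacitidine temporarily discontinued until the toxicity grade returns to less than Grade 3". It does not say how the durvalumab wording should be read.
- Appendix O refers back to Section 7.2.2.

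Some immune-mediated Grade 3 rows of Appendix M pair a hold with a time limit and use the same target grade for both: hepatitis in its lower Grade 3 band (Grade 1 or baseline, 14 days), neurotoxicity (Grade 1, 30 days) and myositis (Grade 1, 30 days; also subject to respiratory signs). The non-immune Grade 3 row adds a second, different grade. That contrast shows where the ambiguity arises, not which grade was intended.

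**Size.** Planned Arm A enrolment is 72/2 + 110/2 = 36 + 55 = 91. The documents give no rate of related non-immune Grade 3 events, of recovery to Grade 2 by day 7, of baseline grade, or of persistence to the next dose. No count can be derived.

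**The case against.** The best defence is that the row works if read as a sequence: hold, then apply a test that separates subjects who may resume from those who must stop. On that reading sentence 2 is either a specific exception to the general hold, or only a sorting test, with sentence 1 still fixing when the hold ends. The Grade 2 row can likewise be confined to events that never exceeded Grade 2. All of this is possible, but the two versions of the defence give opposite answers in course (b), and the text chooses neither. As written, sentence 2 instructs the site to resume.

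The defence does limit the point. The conflict is one narrow course, it needs a baseline below Grade 2, and with 28-day dosing many events may settle before a dose is due.

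A reader might go further and infer that the same event could lead to durvalumab being given, held or stopped. The row does not support that. An event in course (b) meets the test in sentence 2, so sentence 3 cannot reach it.

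A reader might also object that an event peaking at Grade 3 could be re-dosed at a grade at which an event peaking at Grade 2 is held. That presupposes that sentence 2 governs, which is the unsettled question, and it criticises the clinical design of the rule rather than showing a contradiction.

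**Conclusion.** The contradiction is real, safety-relevant and confined to course (b) with the event still at Grade 2 on the day the next infusion is due. The conclusion rests on the plain wording of the row and on the absence of any governing statement elsewhere. The number of Arm A subjects affected is unknown; multiplying the 91 by guessed rates would not supply it.

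A reader might infer that the ambiguity also alters the efficacy evaluable population and the futility analysis, because SAP Sections 5.2.2 and 14.1 exclude Arm A subjects with fewer than 3 durvalumab cycles. The documents do not show this. The exclusion also requires that the subject carried on with azacitidine alone. A delayed dose does not by itself meet both conditions, and neither sentence takes the subject in course (b) off durvalumab. The primary analysis is on the ITT population, which keeps these subjects in any event.

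**What to change.** The sponsor's medical team should reconcile the first two sentences of the Grade 3 row with each other, and state how they relate to the Grade 2 row, so that a site facing course (b) has a single instruction. Which threshold applies is a clinical decision for that team, and none is proposed here.

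The cost is a text correction to Appendix M and a notice to sites. Because the correction touches a hold-and-resume rule, it should go through the usual amendment route in Section 13.5, which requires written IRB/EC approval unless a change is administrative. No additional data or subjects are needed.
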